2.2.3 Part B

Treatment Period 1 of Part B will be conducted in a sentinel cohort of healthy study participants in order to evaluate CBD safety and PK exposure under a single dose of CBD 10mg/kg (fasted conditions).

[figure not shown]
A washout of at least 6 days will occur between Treatment Period 1 and Treatment Period 2. Treatment Period 2 will include 7 days of treatment with open-label PSL treatment. Treatment Period 3 starts after a washout of minimally 6 days for all study participants and includes an ambulatory open-label CBD up titration of 16 days toward a maintenance level of 10mg/kg BID.

Treatment Periods 4 and 5 is a 2-way cross-over, double-blind and placebo-controlled periods with PSL up titrated to a maintenance level of 200mg BID through Day 5 and subsequent down titration until Day 8. A maintenance dose of 10mg/kg BID CBD will occur in-house between Treatment Periods 4 and 5. Cannabidiol down titration starts in Treatment Period 6.

A detailed schematic diagram of Part B of the study is provided in Figure 2-2.

The objectives of Part B are to evaluate the: plasma PK, safety and tolerability of PSL and its metabolites in the presence and absence of CBD; plasma PK of CBD and its metabolites in the presence and absence of PSL; effect of PSL on PD parameters in the presence and absence of CBD; effect of CBD on PD parameters in the presence and absence of PSL.

Figure 2-2: Study schematic – Part B

Note: Follow up will occur between 7 to 10 days after the final dose of CBD.

Note: A WO of at least 6 days will occur following Treatment Period 1 and Treatment Period 2.

BID=twice daily; CBD=cannabidiol; D=day; FU=Follow-up Period; PBO=placebo for PSL; PSL=padsevonil; SD=single dose; W=week

Study participants will be randomized to one of two treatment sequences:

Table 2-2: Treatment Sequences – Part B

Sequence ID	Randomization Sequence	Sequence in Full
1	CBD 10mg/kg BID+PSL(TP4)/ CBD 10mg/kg BID+Placebo(TP5)	PSL(TP2)/CBD(TP3)/ CBD 10mg/kg BID+PSL(TP4)/ CBD 10mg/kg BID+Placebo(TP5)/ CBD(TP6)
2	CBD 10mg/kg BID+Placebo(TP4)/ CBD 10mg/kg BID+PSL(TP5)	PSL(TP2)/CBD(TP3)/ CBD 10mg/kg BID+Placebo(TP4)/ CBD 10mg/kg BID+PSL(TP5)/CBD(TP6)

TP= Treatment Period.

2.3 Determination of sample size

Based on the study PK and PD objectives, the total planned number of healthy study participants will be 44, including 22 evaluable participants for Part A and 22 evaluable participants for Part B.

For Part A, the sample size is based on pragmatic considerations and the ability to detect an ethanol effect on PD assessments (CNS variable). A sample size of 22 evaluable study participants provides 80% power to detect an ethanol effect in a difference in means of 3.96 (% points) for the smooth pursuit test, which is the most sensitive CNS variable to ethanol effects, assuming a SD of difference of 6.0 (% points) based on previous ethanol clamp interaction studies and using a paired t-test 2-sided with a 0.05 significance level. This sample size is also valid for the CBD effect assessment (Part B). The sample size calculation performed does not assess the difference in means between PSL+Ethanol effect vs PSL+Placebo, as the expected difference between the interaction is unknown but similarly a difference of 3.96 (% points) could be detected.

For Part B, a sample size of 22 evaluable study participants is needed to assess the PK interaction between PSL and CBD, and to estimate the mean PSL AUC_{τ} ratio of with/without CBD of 1.5 with a half-width of the CI of 0.3. This sample size has been evaluated with a conditional probability of 90%, assuming an inter-participant coefficient of variation of 45% of PSL AUC_{τ} (observed in study UP0057), correlation of 0.5, 2-sided and $\alpha = 0.05$. A sufficient number of healthy study participants (up to 20) will be selected to have 16 completed study participants.

Regarding the assessment of the single dose formulation of CBD (under fasted conditions) in Part B (study formulation vs Epidiolex formulation from literature data), 16 healthy study participants are required to assess the similarity of the 2 formulations (equivalence range of 50 to 200% based on the high variability of CBD) with a 80% power and assuming an expected geometric mean ratio of AUC and C_{max} between 0.8 and 1.3, and inter-participant CV of 80% (based on CBD literature) and correlation of 0.5.

Sample size computations were performed using SAS version 9.4 (Proc Power).

Drop outs will be replaced at the discretion of the Investigator and Sponsor.

3 DATA ANALYSIS CONSIDERATIONS

3.1 General presentation of summaries and analyses

Each study part will be summarized and analyzed separately.

Statistical evaluation will be performed by ICON PLC with the exception of PD which will be conducted to UCB. The datasets will follow the UCB analysis data model (ADaM) data specifications.

All analyses will be performed using SAS version 9.4 or higher (SAS Institute, Cary, North Carolina, United States). The PK noncompartmental analysis (NCA) will be performed using Phoenix WinNonlin®v6.3 or higher (Certara L.P., Princeton, NJ, USA) for pharmacokinetics parameters estimation. All non-PD TFLs will be produced by ICON PLC SAS programming (Early Phase).

Continuous variables will be summarized by phase (defined in [Section 3.5](#)), treatment and timepoint (where applicable) including number of study participants (n), mean, standard deviation (SD), median, minimum, maximum and 95% confidence intervals (CI) for the mean. Geometric coefficient of variation (geoCV), geometric mean and 95% confidence interval (CI) for the geometric mean will also be presented in the descriptive statistics for the PK concentration data and PK parameters of; PSL and its metabolites () and

██████████), and CBD and its active metabolite. In all outputs the confidence limits will be restricted to the possible values that the variable can take.

Categorical variables will be summarized by phase, treatment and timepoint (where applicable) with frequency counts and percentages.

3.2 General study level definitions

3.2.1 Study day

For Part A, study day consist of Day -1 (prior to Treatment Period 1) to approximately Day 16 (last day of Treatment Period 6).

For Part B, study day consists of Day -1 (prior to Treatment Period 1) to approximately Day 53 (last day of Treatment Period 6).

Relative day will not be used in this study. Instead refer to [Section 3.2.1](#) for use of Study Day.

3.3 Definition of Baseline values

Measurement-specific Baseline timepoints are presented in Table 3–1.

Table 3–1: Definition of Baseline

Measurement	Definition of Baseline
Hematology, serum chemistry, urinalysis	
For Part A, baseline is defined as the visit at which study participants were randomized to one of the four treatment sequences i.e. Day -1 prior to Treatment Period 1.
 
For Part B, baseline is defined as Day -1 prior to Treatment Period 2.
 
For both study parts, if Day -1 is missing or multiple assessments occur, the last measure prior to dosing will be used.

Vital Signs	
For Part A, baseline is defined as predose on Day 1 of Treatment Period 1.
 
For Part B, baseline is defined as predose on Day 1 of Treatment Period 2.
 
For both study parts, if predose on Day 1 is missing or multiple assessments occur, the last measure prior to dosing will be used.

ECG	
For Part A, the mean of the last three measurements predose on Day 1 of Treatment Period 1 will be taken as baseline.
 
For Part B, the mean of the last three measurements predose on Day 1 of Treatment Period 2 will be taken as baseline.
 
For both study parts, if less than three replicates are available predose, the mean of the available replicates (predose) will be taken as baseline.

C-SSRS	For both study parts, separate baseline questionnaire for C-SSRS.

Measurement	Definition of Baseline
PD variables	For both study parts, baseline for change from baseline summaries and tables is defined as the average of the two values measured at predose of given day. Baseline definition for the model is defined in Section 10.1.2 .

The change from Baseline to any subsequent post-Baseline visit will be calculated as the simple difference between that post-Baseline visit's value and the Baseline visit value, as below:

$$\text{Post Baseline Visit Value} - \text{Baseline Visit Value}$$

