9.2 General statistical considerations

All analyses will be performed using SAS[®] Version 9.4 or later (SAS Institute, Cary, NC, USA).

For continuous variables, summary statistics will include number of study participants, mean, median, standard deviation, minimum, and maximum. Categorical endpoints will be summarized using number of study participants, frequency, and percentages. Missing data will not be imputed.

If not otherwise stated, Baseline will be the last assessment prior to dosing. Measurement of specific Baseline values will be described in the SAP.

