11.3 Clinical laboratory evaluations

All laboratory results (clinical chemistry, hematology and urinalysis) outside the normal ranges will be listed by study participant, phase, treatment sequence, timepoint and parameter including most recent treatment received, changes from Baseline for numeric variables, the reference ranges and a flag to indicate whether values are below the lower limit of the reference range or above the upper limit of the reference range. The listing will include any laboratory value out of normal range at the timepoint it occurred only.

Separate listings of clinical chemistry and hematology laboratory results outside the normal ranges will be provided. These listings will include all data for a parameter for which a participant has at least one abnormal value during the study.

Urinalysis results will be listed by study participant, phase, treatment and timepoint including changes from Baseline for numeric variables, the reference ranges and flags for values outside the normal ranges.

A separate listing for laboratory results meeting the criteria for potential drug-induced liver injury (PDILI) will be provided. The listing will present the study participant who meets one or more of the following criteria for PDILI at any time point:

- Alanine aminotransferase (ALT) or aspartate aminotransferase (AST) $\geq 3x$ upper limit of normal (ULN)
- Alkaline phosphatase $\geq 2x$ ULN
- Total bilirubin increase $\geq 2x$ ULN

Clinical chemistry and hematology parameters will be summarized by phase, treatment and timepoint for both absolute values and changes from Baseline.

Laboratory variables will be grouped according to the laboratory function panel (Table 10-1) and categorized as normal, high or low, if applicable, based on the reference range supplied by the analytical laboratory. For selected variables that are identified in Table 10-1 the change in category from Baseline will be presented in shift table at all post-Baseline time points.

Any additional laboratory variables not included in the outputs described previously will be listed separately. These will include the following:

- Serology
- Alcohol breath test
- Serum pregnancy test (for women of childbearing potential)
- Urine toxicology screen

Figures of mean and mean change from Baseline may be presented for selected laboratory variables that will be identified at the DEM.

Table 11-1: Laboratory measurements

Laboratory Assessments	Parameters		

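### Part B has no baseline before cannabidiol (CBD) dosing for laboratory, vital-sign and ECG data, so CBD Phase change from baseline is undefined or taken against a later, post-CBD value

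*SAP*

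**What the plan says.** SAP 3.3, Table 3-1, gives one Part B baseline for each of three safety measures:

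- Laboratory tests: "For Part B, baseline is defined as Day -1 prior to Treatment Period 2".
- Vital signs: "For Part B, baseline is defined as predose on Day 1 of Treatment Period 2".
- ECG: "For Part B, the mean of the last three measurements predose on Day 1 of Treatment Period 2 will be taken as baseline".

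None of these is limited to a phase, and no Treatment Period 1 baseline is given. Two measures are outside the point. The suicidality scale has its own reference ("For both study parts, separate baseline questionnaire for C-SSRS"), and the pharmacodynamic variables use predose values from the same day. In Part A, by contrast, the laboratory, vital-sign and ECG baselines are all taken before any study dose.

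The laboratory row has a fallback: "For both study parts, if Day -1 is missing or multiple assessments occur, the last measure prior to dosing will be used". The vital-signs row has a similar one. Below the table, the formula is introduced with "The change from Baseline to any subsequent post-Baseline visit will be calculated as the simple difference".

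SAP Table 3-3 maps Treatment Period 1 to its own CBD Phase. SAP 11.3 then requires chemistry and hematology to be "summarized by phase, treatment and timepoint for both absolute values and changes from Baseline". SAP 11.4.1 and 11.4.2 ask for changes from baseline by phase for vital signs and ECG. They also ask for vital-sign abnormality flags that depend partly on change, and for QTcF change categories at each timepoint.

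**The concern.** Protocol 4.1.2 runs Treatment Period 1 in a sentinel cohort to look at CBD safety as well as exposure. The natural safety question is how each person's laboratory, blood pressure and QTcF values moved from before the dose to after it. The SAP orders tables that should answer this. Its only Part B baseline, however, is taken after the CBD dose and after a washout of at least 6 days.

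At stake is whether the CBD Phase change tables, QTcF change categories and change-based vital-sign flags can be produced at all. If they are produced, the question is whether they mean what their titles say. The programmer would have to choose a reference that the SAP does not name, and two programmers could choose differently.

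**Working it through.** No sample size, power or error rate is involved, so there is no stated figure to reproduce. The check sets the rules against the schedule and adds one side calculation.

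**Step 1: order of events for a sentinel participant** (Protocol Table 1-5, Protocol 4.1.2, SAP Table 3-3).

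- Treatment Period 1, Day -1: laboratory tests.
- Day 1: CBD single dose; vital signs and ECG.
- Day 2: laboratory tests, vital signs and ECG.
- Optional Days 15 and 16: a second CBD dose and assessments.
- Washout of at least 6 days.
- Treatment Period 2, Day -1 or Day 1 predose: the only Part B baseline.

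Every Treatment Period 1 visit therefore precedes the baseline.

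**Step 2: apply the formula literally.** Change is defined only for visits after the baseline visit. No Treatment Period 1 visit qualifies, so CBD Phase change is undefined. SAP 11.3, 11.4.1 and 11.4.2 nevertheless order it by phase.

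**Step 3: apply the only available baseline anyway.** Let y0 be the pre-CBD value, y1 the on-CBD value and b the Treatment Period 2 baseline. The quantity wanted is y1 − y0. The quantity computed is

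y1 − b = (y1 − y0) − (b − y0).

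The error is b − y0. If the person has returned exactly to the starting value, b = y0 and the error is zero. If a shift is still fully present, b = y1 and the reported change is 0. In between, drift and measurement noise from a later visit enter the result.

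**Step 4: how much CBD is left at the later baseline?** Protocol 4.2.2 gives a single-dose oral half-life of about 1 to 2 days. Assuming first-order elimination, the fraction remaining is 0.5^(days / half-life):

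- 6 days, half-life 1 day: 0.5^6 = 1.6%.
- 6 days, half-life 2 days: 0.5^3 = 12.5%.
- 8 days (roughly the Table 3-3 day count from the Day 1 dose), half-life 1 day: 0.5^8 = 0.4%.
- 8 days, half-life 2 days: 0.5^4 = 6.3%.

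The later baseline follows CBD exposure but comes after most of the drug has gone. This limits carry-over into the baseline used for the later phases. It does not supply a reference for the CBD Phase.

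**Step 5: the fallback.** It does not say which dosing it means. If it means Treatment Period 2 dosing, the last available value could be from Treatment Period 1 Day 2 (or Day 16), about a day after CBD. If it means the first study dose, the value is pre-CBD. For someone with no Treatment Period 2 data, the SAP does not settle the matter.

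**Step 6: who is affected.** Protocol 1.1.6 and 4.2.2 require at least 16 participants in this cohort, and Protocol 9.10 allows up to 20 to be selected.

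**The case against.** The strongest reply is that the SAP nowhere tells anyone to subtract a later value from an earlier one. That is right. The formula covers only later visits, so the backward difference is one possible programming outcome and not an instruction. The literal alternative, however, is a set of ordered outputs with nothing defined to fill them.

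A Treatment Period 2 baseline also has an evident use. Some participants enter Part B there (Protocol Table 1-6, footnote a), so it is the one point before padsevonil (PSL) dosing that all Part B participants share. This supports keeping it for the later phases and says nothing for the CBD Phase.

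Nor does the SAP breach the protocol's rule that "Baseline will be the last assessment prior to dosing". Protocol 9.2 applies that rule only where nothing else is stated, and leaves specific baselines to the SAP.

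Much CBD safety information needs no baseline: adverse events, out-of-range laboratory listings, liver-injury criteria based on the upper limit of normal, and absolute QTcF categories. That stands and limits the harm.

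Three stronger readings are tempting, and the documents do not support them:

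- **The laboratory shift tables are wrong.** SAP 11.3 restricts them to time points after baseline, so Treatment Period 1 is outside them.
- **The decision to continue Part B is distorted.** Protocol 4.1.2 and SAP 4.3 place that decision before Treatment Period 2 starts, when no such baseline exists. Neither document makes change-from-baseline tables an input to it.
- **Anyone who stops after Treatment Period 1 necessarily lacks a baseline in the tables.** The fallback might supply one. It is also unclear whether such people are in the Safety Set, which requires randomization: Protocol 6.3 allocates the number before study drug is given, but the SAP's Part B sequences begin at Treatment Period 2.

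**Conclusion.** Wrong as written. The stated Part B baseline rule for laboratory tests, vital signs and ECG cannot support the CBD Phase change-from-baseline outputs that the SAP itself orders. Those changes are either undefined or measured against a later, post-CBD value.

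The effect falls on the reported CBD safety data of the sentinel cohort, at least 16 participants. No primary endpoint is touched: Part A's is pharmacodynamic and Part B's are pharmacokinetic.

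A reader might infer that a lasting CBD effect is being hidden in the baseline for the whole of Part B. The documents show no such effect. The 1.6% to 12.5% remaining at 6 days makes material carry-over unlikely, assuming first-order elimination, the protocol's half-life, and an effect that fades with the drug. The size of any error in an individual CBD Phase change (b − y0) cannot be derived from the documents.

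**What to change.** In SAP Table 3-1, add a CBD Phase entry to the laboratory, vital-signs and ECG rows:

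- Baseline is the last value before the first CBD dose of Treatment Period 1: Day -1 for laboratory tests, Day 1 predose for vital signs and ECG.
- Protocol Table 1-5 does not time the Day 1 vital signs and ECG relative to the dose. If a Day 1 assessment was not predose, use the last earlier pre-CBD value.
- If the optional Day 15 dose is given, use the same pre-CBD value for it.
- State which dosing the fallback refers to.
- Keep the Treatment Period 2 baseline for the PSL and Interaction Phases.

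The cost is about one line per row and some programming. No new assessment is needed, because Protocol Table 1-5 already schedules Screening and Day -1 laboratory tests, and Screening and Day 1 vital signs and ECG.

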3.4 Protocol deviations

Important protocol deviations (IPD) are deviations from the protocol which potentially could have a meaningful impact on study conduct or on either the primary outcome or key secondary outcome for an individual study participant. The criteria for identifying such protocol deviations will be defined within the protocol deviation specifications document.

Important protocol deviations will include the following categories:

- Inclusion/exclusion criteria deviations
- Administration of prohibited concomitant medications
- Deviations relating to withdrawal criteria
- Visit schedule deviations
- Study drug administration deviations (including incorrect treatment received, handling and storage deviations and incorrect dosage received) and any vomiting episode(s) (that could impact PK concentrations)
- Procedural noncompliance
- Missing data

All IPDs will be reviewed as part of the ongoing data cleaning process and data evaluation. After all data have been verified/coded/entered into a database, a data evaluation meeting (DEM) will be performed.

At least one DEM will be performed at the following time:

- Prior to the final analysis after all data have been verified/coded/entered into the database

Additional DEMs may be conducted as deemed necessary.

The purpose of these DEM reviews will be to review all protocol deviations, define the analysis sets, and check the quality of the data. The reviews will also help decide how to manage problems in the study participants' data (e.g. missing values, withdrawals and protocol deviations).

Accepted deviations from scheduled time points will be described in the appropriate documents and included in the Study Master File. After the pre-analysis review, resolution of all issues, and documentation of all decisions (including inclusion into each of the analysis sets) at the final DEM, the database will be locked.

3.5 Analysis Sets

The following analysis sets apply and will be created separately for each study part.

3.5.1 All Study Participants

All Study Participants will consist of all participants who have signed the Informed Consent form (ICF). This set was previously referred to as Enrolled Set in the Study Protocol.

3.5.2 Safety Set

The Safety Set (SS) will consist of all study participants who are randomized and have received at least 1 dose (any amount) of study medication. Safety variables will be analyzed using the SS.

It is expected that study participants will receive treatment as randomized; hence, safety analyses will be based on the randomized treatment group. However, if after unblinding it is determined that study participants received the incorrect treatment (i.e. not as per the randomization schedule), then for safety analyses study participants will be allocated to the actual treatment they received (as-treated) for the data summaries.

3.5.3 Full Analysis Set

The Full Analysis Set (FAS) consists of all study participants that were randomized, received study medication, and had at least one valid post-baseline primary PD assessment observation. It is intended that study participants will be classified according to the treatment which was actually received.

3.5.4 Pharmacokinetic Set

The Pharmacokinetic Set (PKS) consists of all study participants that received at least one dose of active study drug and have at least one observable PK measurement. If a study participant in the PK set is missing individual timepoints or are otherwise unobservable will be included in the PK set but those timepoints will be omitted from the PK summaries, as appropriate.

3.6 Treatment assignment and treatment groups

3.6.1 Part A

For all analyses (where applicable) the results will be presented by phase and treatment. For summary tables, results from Treatment Period 3 and 6 will be presented by PSL. Sequence in full will be used where applicable (defined in [Section 2.2.2](#)).

Phase, phase day, treatment (for listings and tables) and the corresponding treatment period and day from the protocol are defined in Table 3-2.

Table 3–2: Definition of Phase - Part A

Protocol Treatment Period	Protocol Treatment Period Day	Phase	Phase Day	Treatment for Listings	Treatment for Tables
Screening	-28 to -2	Screening	-28 to -2	N/A	N/A
1	-1 to 2	Ethanol Phase	-1 to 2	Ethanol/Placebo	Ethanol/Placebo
2	1 to 2	Ethanol Phase	3 to 4	Ethanol/Placebo	Ethanol/Placebo
Washout Period	-	Ethanol Phase	5 to 6	Ethanol/Placebo	Ethanol/Placebo
3	-1	Interaction Phase	-1	Ethanol/Placebo	Ethanol/Placebo*
3	1	Interaction Phase	1	PSL up-titration	PSL
3	2 to 4	Interaction Phase	2 to 4	PSL maintenance	PSL
4	5	Interaction Phase	5	PSL+Ethanol/PSL+Placebo	PSL+Ethanol/PSL+Placebo
4	6	Interaction Phase	6	PSL maintenance	PSL
5	7	Interaction Phase	7	PSL+Ethanol/PSL+Placebo	PSL+Ethanol/PSL+Placebo
5	8	Interaction Phase	8	PSL tapering	PSL
6	9 to 10	Interaction Phase	9 to 10	PSL tapering	PSL
Follow-up	-	Follow-up	17 or 20	N/A	N/A

- = Day not specified in protocol; * If assessments are summarized by treatment, phase and day, then data will be presented as: PSL, Interaction Phase, Day -1. If assessments are summarized by treatment, then data from Day -1 will attribute to either Ethanol or Placebo e.g. if an AE occurs on Day -1, then the AE will be summarized where treatment is Ethanol or Placebo since this is the most recent treatment received.

